9 SECURITY ASSESSMENT

9.1 Security endpoints

- Frequency of side effects;
- Frequency of serious side effects;
- Frequency of clinically significant changes in laboratory parameters and vital signs after infusion of the study drug;
- Dynamics of laboratory parameters.

9.2 Definitions concerning safety assessment.

Adverse event

Adverse event (AE) is any adverse change in the health of a patient or subject who has been administered a drug, regardless of the causal relationship with its use.

AE can be any adverse and unintentional change, symptom or disease, the time of occurrence of which does not exclude a causal relationship with the use of the drug, regardless of the presence or absence of a relationship with the use of the drug.

AEs may be abnormal laboratory parameters, first-time symptoms, or diseases that are related to the use of the drug, or if they existed before treatment of a condition whose severity or frequency increased after administration of the study drug.

Any medical condition present at the time of the patient's screening, but not deteriorating during the study, should not be recorded as an AE. However, if this medical condition worsens at any time during the study, it should be recorded as an AE.

Medical interventions, such as surgeries, diagnostic and treatment procedures, are not AEs, but they are interventions to treat the relevant medical condition and should be registered as a treatment for ANs.

Deviations from the norm of laboratory parameters

Any deviation from the norm of the laboratory indicator, which appeared for the first time, or the degree of severity, the frequency of which has increased compared to baseline, and meets at least one of the following criteria, must be recorded as AE:

- Requires medical intervention or diagnostic procedure;

- Leads to the cancellation of the study drug;
- Accompanied by complaints or symptoms, or causes them;
- Considered by the researcher as "clinically significant".

If there is any doubt as to whether a clinical event is an AE, it should be recorded as an AE.

Adverse reaction

Adverse reaction (AR) is an adverse reaction of the body associated with the use of a medicinal product (study drug), which implies the presence of at least a possible relationship with the use of a suspected drug (study drug).

During the study period, the investigator or study staff should conduct surveys and record information on adverse events / reactions as defined in this section of the protocol.

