
Unforeseen adverse reaction

Unforeseen AR - adverse reaction, nature, severity or outcome of which does not correspond to the information contained in the general characteristics of the medicinal product (instructions for medical use) or in the researcher's brochure (for unregistered medicinal product).

| Bioven | Page 62 |
|----------------------------|--------------------------------|
| Trial Code: 2021-BV-ITP-BP | Version 1.4 from July 03, 2023 |

Serious adverse event

Serious adverse event (SAE)- Adverse medical event that leads to death, threatens life, requires hospitalization or continuation of hospitalization, leads to permanent or severe disability or incapacity, congenital anomalies or malformations, requires medical intervention to prevent the development of these conditions.

Page 62

Death- is usually the result of the underlying clinical phenomenon that causes it. Therefore, the cause of death should not be considered serious. The only exception is "sudden death", when its causes have been established. In this case, "sudden death" should be considered AE, the reason for its "seriousness" - its "lethality".

Threat to life- the term "threat to life" is defined as an AE during which there was a threat to the patient's life. This does not mean any AE that can hypothetically lead to death in the case of its increased complexity.

Hospitalization- any adverse event leading to hospitalization or continuation of hospitalization will automatically be considered serious if it does not meet any of the non-inclusion criteria listed below:

hospitalization lasts less than 12 hours or hospitalization is planned in advance (it is an optional or planned operation, which was agreed upon before the start of this study).

Disability is defined as a significant impairment of a person's ability to perform daily functions, such as a congenital anomaly / malformation.

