9.3 Detection and registration of AE

Detection and registration of SAE begins from the moment of signing the informed consent and lasts until the end of the patient's participation in the study.

Detection and registration of AE begins with the introduction of the drug and lasts until the end of the patient's participation in the study.

AE that occur between screening and administration of a drug, but does not considered as a SAE should be recorded as a medical history.

All AEs arising from the administration of the drug reported by the patient or detected during observation, physical examination and other diagnostic procedures must be registered in the AE Reporting Form attached to the Individual Registration Card.

Laboratory parameters will be evaluated during screening and throughout the study.

Information on any AE observed during the study period, from the first use of the study drug to the end of its use, is recorded in the patient's medical history / outpatient card and in the IRF registration section. All AEs are subject to registration, regardless of the severity or the presence of a causal relationship with the investigational medicinal product.

As AE should be classified:

- exacerbation of previous diseases;
- · increase in the frequency or intensity of diseases or episodic phenomena observed earlier:
- diseases detected or diagnosed after the start of the study drug, even if it is possible before the patient's participation in the study;
- long-term, persistent disease or symptoms that were in the initial stage, the severity of which increased after the start of the patient's participation in the study;

- the appearance of new signs or an increase in the severity of the signs and symptoms of diabetes mellitus, which require urgent therapy, hospitalization, surgery and / or other intervention;
- clinically significant abnormalities detected by laboratory diagnostics or other examinations after the start of the study drug or available at baseline, the severity of which increased on the background of the study drug.

AS a AE should not be classified:

- 1. diseases or pathologies detected or diagnosed before the use of the investigational medicinal product, the severity of which does not increase;
- 2. situations in which there is no medically unfavorable event (for example, hospitalization for the planned surgery);
- overdose of any of the studied drugs or concomitant drugs without unwanted signs or symptoms;

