- 4. any clinically significant deviation of the laboratory indicator from the norm, detected before the first use of the study drug;
- 5. signs and symptoms observed during the study, which are associated with insufficient effectiveness of treatment.

The study will monitor the occurrence of any adverse events (AE). Table 1 presents the tolerance assessment scale.

| Category | Category description |
|----------------|--|
| Good | At objective inspection in dynamics any pathological changes or clinically significant deviations does not find, data of laboratory inspection do not change reliably and do not go out of norm, the patient does not feel the side reactions. |
| Satisfactory | At objective inspection in dynamics insignificant changes which have temporary character and do not demand change of the scheme of treatment and carrying out additional medical actions come to light. and / or laboratory test data deviate slightly from normal. and / or there are minor side effects that do not cause serious problems to the patient and do not require discontinuation of the drug |
| Unsatisfactory | At objective inspection in dynamics the pathological changes demanding drug cancellation and carrying out additional medical actions come to light. and / or laboratory test data undergo clinically significant negative changes, which entails the need for additional examination and interpretation of data and / or there is an undesirable side effect that has a significant negative impact on the patient's condition, requiring discontinuation of the drug and the use of additional medical measures |

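### Sections 9.2 and 9.3 give opposite instructions on whether a new or worse bleed is an adverse event, so the AE frequency can be understated

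*Combined protocol and SAP*

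**What the plan says.** Three rules point towards recording a bleed as an AE:

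- Section 9.2, on a condition already present at screening: "if this medical condition worsens at any time during the study, it should be recorded as an AE".
- Section 9.3, first list (events to be classified as AEs): "exacerbation of previous diseases", and also "long-term, persistent disease or symptoms that were in the initial stage, the severity of which increased after the start of the patient's participation".
- Section 9.2, general rule: "If there is any doubt as to whether a clinical event is an AE, it should be recorded as an AE".

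One rule points the other way. Item 5 of the second list in section 9.3 (events not to be classified as AEs) names "signs and symptoms observed during the study, which are associated with insufficient effectiveness of treatment". It carries no exception.

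On seriousness, section 9.2 defines an SAE as an "Adverse medical event that leads to death, threatens life, requires hospitalization or continuation of hospitalization", among other outcomes. It then says that "any adverse event leading to hospitalization or continuation of hospitalization will automatically be considered serious", subject to short or pre-planned stays, and it explains threat to life as a kind of AE. Section 9.9 requires the sponsor to be told of any SAE within 24 hours.

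Section 8.2 lists the percentages of AEs and SAEs as the safety endpoints. The same section makes bleeding one of the criteria for non-response, loss of response and loss of complete response.

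**The concern.** Every enrolled patient has ITP, so bleeding after treatment is a worsening of the disease the patient came with. By the protocol's own efficacy definitions it is also evidence that treatment has failed or stopped working. The first description makes it an AE and the second takes it out of the AE record. Two investigators seeing the same bleed could classify it differently, and each could cite section 9.3 in support.

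The trial has a single arm, so the absolute AE and SAE frequencies are the safety result. No control arm is present in which under-recording would show. If some bleeds are left out under item 5, the reported AE frequency is too low, and a reader of the safety tables could not tell.

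**Working it through.** No arithmetic applies. The plan states no figure on this point, so the check sets the passages side by side for one event: a new bleed, or one worse than at entry, after the infusions.

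1. **Is it a worsening of a pre-existing condition?** Yes. ITP is an inclusion criterion (section 5.1). Section 9.2 and the first list in 9.3 then require an AE record.

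2. **Is it a sign associated with insufficient effectiveness?** By the protocol's definitions it can be. Under section 8.2 bleeding can establish non-response or, in a patient who had responded, loss of response. Item 5 then says that it is not an AE.

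3. **Does any text rank the two rules?** None does. Item 5 does not mention worsening of disease, and the first list does not mention lack of effect.

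4. **Does the rule on doubt settle it?** In part. It favours recording when the investigator is unsure. An investigator who is confident that the bleed reflects lack of effect has no doubt to resolve and meets a direct instruction not to record.

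5. **Does the event still reach the SAE count?** This is less clear. The general definition in 9.2 is worded by outcome and can be read as standing apart from item 5. The explanations of threat to life and hospitalization are worded in terms of an AE, and item 5 makes no exception for serious events. A serious bleed held not to be an AE could therefore miss the SAE count and the 24-hour notice. The text permits this reading without requiring it.

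6. **Is the bleed reported elsewhere?** Section 6.5.5 grades hemorrhagic syndrome on a severity scale, section 6.6 has it examined at each visit, and section 3 makes its evaluation a study task. The scale is not named among the endpoints in 8.1, 8.2 or 9.1, or in the safety analysis in 10.3.4. In the efficacy endpoints bleeding sits inside yes/no composites with platelet counts, so the number of bleeds cannot be recovered from those percentages.

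7. **Is there a patient for whom both routes fail?** Yes. Sections 5.3 and 10.4 leave patients without a full course out of the efficacy analysis. If such a patient bleeds and the bleed is put under item 5, it can appear in neither the efficacy percentages nor the AE frequency.

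**The case against.** The strongest reply is that the protocol leans towards recording. Section 9.2 says to record in doubt, and two conflicting lists are themselves a reason for doubt. Section 9.3 requires AEs found at physical examination to be registered, and the check for bleeding is part of that examination. This makes omission less likely, but it leaves the confident investigator of step 4 with an instruction not to record.

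A reader might infer that serious bleeds will drop out of SAE reporting just as bleeds drop out of the AE count. The documents do not support that. The general SAE definition rests on outcome, and SAE detection starts at consent, before AE recording begins (section 9.3), so SAEs are not simply a subset of the post-dose AE list. Item 5 also speaks of signs and symptoms, while section 9.4 has a known diagnosis registered as the AE. A hospitalised gastrointestinal bleed can reasonably be read as reportable. The SAE consequence is possible but not established.

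A reader might also infer that the trial loses its most important harm from view. It does not: bleeding remains in the visit data and in the efficacy composites. What is unclear is its place in the AE and SAE frequencies.

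It is tempting to size the effect from the 78% reference response rate in section 10.2: 40 × (1 − 0.78) = 8.8 non-responders, or 22 percentage points if all of them bled. That is not a usable bound. The documents do not say how many non-responders bleed. Responders who bleed later could also fall under item 5. A bleed changes the share of patients with any AE only in a patient who has no other AE.

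Finally, the open-label design adds little. With one arm there is no between-arm comparison for selective labelling to bias.

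**Conclusion.** The contradiction is real and stands in current text. A new or worse bleed is covered both by a rule that requires an AE record and by one that forbids it, and the protocol does not say which prevails. The AE frequency can be understated; the SAE count and 24-hour reporting may be. The text allows omission and does not compel it, and the rule on doubt reduces the risk without removing it.

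No magnitude can be stated, because the documents give no bleeding rate. The conclusion rests on the wording alone and on one reading: that a bleed which section 8.2 counts towards non-response or loss of response is a sign associated with insufficient effectiveness under item 5. The point should be corrected, since it touches a named safety endpoint and costs little to settle.

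**What to change.** Reconcile sections 9.2 and 9.3 by adding to item 5 that it does not apply to:

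- new bleeding;
- bleeding worse than baseline on the hemorrhage scale in section 6.5.5;
- any event that meets a seriousness criterion in section 9.2.

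State that all of these are recorded as an AE or SAE whatever the presumed role of lack of effect. Leave the laboratory-abnormality rules in 9.2 and 9.3 as they are. Rewriting item 5 around platelet counts without symptoms would set up a second conflict, because those rules already make clinically significant or worsened laboratory findings AEs.

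In section 10.3.4, add a tabulation of AEs with and without bleeding events, so that a reader can separate bleeding from other harms.

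The cost is a sentence or two in 9.3 and one more table. The reported AE rate may be higher. The change concerns recording and reporting only and does not alter treatment.

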3. PURPOSE AND OBJECTIVES OF RESEARCH

Objective: To evaluate the efficacy, safety and tolerability of Bioven in patients with chronic primary immune thrombocytopenia, with evidence of non-inferiority compared to the literature data regarding the level of effectiveness of existing IVIG products.

Tasks of study:

- To evaluate the proportion (%) of patients who achieved the response (R) during the study, platelet count> 30x10⁹ / 1 and at least double their initial number, as confirmed by at least 2 blood tests performed every 7 days; absence of bleeding) during therapy with the studied drug Bioven.
- To evaluate the effeciency of the studied drug Bioven in comparison with the literature data
- To evaluate the presence and severity of hemorrhagic syndrome as a result, which is included within 4 weeks after starting therapy;
- To evaluate the proportion (%) of patients who achieved a complete response (CR) during the study (platelet count> 100 x 10^9 / l, confirmed by at least 2 blood tests performed every 7 days; no bleeding) during treatment with the study drug Bioven.
- To evaluate the proportion (%) of patients who did not respond (NR) during the study with a platelet count $<30 \times 10^9$ / L or less than a 2-fold increase in platelet count from baseline. This must be confirmed by at least 2 blood tests with a difference of one day, or the presence of bleeding during therapy with the study drug Bioven.
- To evaluate the proportion (%) of patients who lost the response (R) during the study (a decrease in platelet count (<30 x 10^9 / L, or less than twice the initial or bleeding. Platelet counts should be confirmed at least twice with an interval of 1 day).
- To evaluate the proportion (%) of patients who lost a complete response (CR) during the study, a decrease in platelet count, $<100 \times 10^9$ / l, or the occurrence of bleeding. Platelet counts should be confirmed at least twice with an interval of 1 day).
- To determine the time from the start of treatment with the study drug Bioven to the onset of the response (R);
- To determine the time from the start of treatment with the studied drug Bioven to the onset of a complete response (CR);
- To set the duration of the response (R);
- To set the duration of the complete response (CR);
- To evaluate the frequency and severity of possible adverse events/adverse reactions (AE/AR).

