8.2 Secondary efficiency endpoints

Part (percent) of patients with a complete response (CR).

CR is determined according to the following criteria:

- Patients with CR: platelets count > 100 x 10^{9} /L, which is confirmed by 2 blood tests performed at least 7 days apart and the absence of bleeding;

Part (percent) of patients with no response (NR).

NR is determined according to the following criteria:

- Patients with NR: platelet count $< 30 \times 10^{9}$ /L or less than two-fold increase of baseline platelet count. This must be confirmed by at least 2 blood tests performed approximately 1 day apart, or the presence of bleeding;

Part (percent) of patients with loss of response (loss of R).

Loss R is determined according to the following criteria:

- Patients with loss R: a decrease platelet count < 30×10^9 /L or less than two-fold increase of baseline platelet count, or the occurrence of bleeding. Platelet counts confirmed at least 2 blood tests performed approximately 1 day apart.

Part (percent) of patients with loss of complete response (loss of CR).

CR loss is determined according to the following criteria:

- Patients with loss of CR: decrease platelet count < 100 x $10^9/L$, or the occurrence of bleeding. Platelet counts confirmed at least 2 blood tests performed approximately 1 day apart.

Time (in days) from treatment start to onset of a response (R); Time (in days) from treatment start to onset of a complete response (CR); Duration (in days) of response (R); Duration (in days) of complete response (CR);

Secondary efficacy endpoints are transformed into corresponding efficacy variables

Safety

- Frequency (percent) of adverse events

- Frequency (percent) of serious adverse events

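### Section 9.3 item 5 conflicts with the other AE rules, so a new or worse post-dose bleed can be left out of the AE frequency, and 10.3.4 names no bleeding output

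*Combined protocol and SAP*

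**What the plan says.** Section 9.3 has two lists. The list of what is not an AE ends with item 5: "signs and symptoms observed during the study, which are associated with insufficient effectiveness of treatment". The list of what is an AE includes "exacerbation of previous diseases" and "increase in the frequency or intensity of diseases or episodic phenomena observed earlier". Section 9.2 adds that a condition present at screening becomes an AE if it worsens, and gives a rule for uncertain cases: "If there is any doubt as to whether a clinical event is an AE, it should be recorded as an AE".

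On efficacy, section 8.1 requires absence of bleeding for a response. Section 8.2 lets no response be met by low counts "or the presence of bleeding", and defines loss of response and loss of complete response by falling counts "or the occurrence of bleeding".

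Section 3 lists as a task: "To evaluate the presence and severity of hemorrhagic syndrome as a result, which is included within 4 weeks after starting therapy". Section 6.5.5 requires an examination for hemorrhagic syndrome and supplies a severity scale. Section 10.3.4 plans AE and SAE frequencies with MedDRA lists, laboratory results, the Coombs test and hemolysis, and vital signs. It does not name bleeding or the hemorrhagic grade.

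**The concern.** In ITP, a bleed after dosing is both a worsening of the disease under treatment and a sign that treatment has not worked. Two sets of rules therefore claim the same event, one making it an AE and one making it not an AE. No sentence says which prevails over the other, and item 5 has no carve-out for bleeding or for serious events.

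What is at stake is the safety description. AE and SAE frequencies are the safety endpoints listed with the efficacy endpoints in section 8.2, and section 2.1 gives prevention of massive bleeding as the main goal of treatment. If bleeds can be left out of the AE count and no other safety table shows them, a report that follows the plan may say little about the harm that matters most in this disease.

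**Working it through.** The plan states no bleeding rate and no expected AE frequency, so there is no figure to reproduce. The check is a reading of the rules, followed by the effect of one reclassified patient.

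**1. Two routes for one event.** Take a patient with a few petechiae before the first infusion who later develops gum bleeding.

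| Route | Rule | Result |
|---|---|---|
| A | 8.2: bleeding is a criterion for no response or loss of response; 9.3 item 5: signs of insufficient effectiveness are excluded | Not an AE |
| B | 9.2: a screening condition that worsens; 9.3: exacerbation or greater intensity of earlier disease | AE |

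Both routes use the current text.

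**2. The doubt rule.** It sends uncertain cases to route B. It acts only on an investigator who is in doubt. One who goes from 8.2 to item 5 has a direct rule and need not be in doubt.

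**3. Serious bleeds.** The SAE definition in 9.2 speaks of an adverse medical event and has no lack-of-effect exclusion. SAE registration also starts at consent, before AE registration starts. Both favour reporting. Against this, threat to life "is defined as an AE during which there was a threat", and the hospitalization clause is likewise worded for adverse events, so a literal reader could carry item 5 over. That is a possible reading and a weaker one.

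**4. Where a bleed handled by route A would still appear.**

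| Patient | Efficacy results | Safety results |
|---|---|---|
| In the efficacy set | Through R, CR, NR and the loss endpoints | Tolerability category only |
| Incomplete course (outside efficacy under 5.3) | No | Tolerability category only |
| Full course, but visits missed or a significant deviation | No if 10.4 is followed (per-protocol only); 5.3 would keep those who drop out in follow-up | Tolerability category only |

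The tolerability scale following 9.3 combines examination findings, laboratory changes and side effects in three categories, so it does not identify a bleed. Section 10.3.4 does not name the scale.

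**5. Size per patient.** Inputs: N = 40 (section 4.1) and N = 36 (section 10.2). Assumption: the frequency is the percentage of dosed patients with at least one AE, and the bleed is the patient's only event.

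- Change per patient = 100/N
- 100/40 = 2.5 points; 100/36 = 2.8 points

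If, as an assumption only, 1 to 3 patients were affected, the AE frequency from these patients would be:

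| Patients | Route A | Route B, N = 40 | Route B, N = 36 |
|---|---|---|---|
| 1 | 0% | 2.5% | 2.8% |
| 2 | 0% | 5.0% | 5.6% |
| 3 | 0% | 7.5% | 8.3% |

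**The case against.** The best defence is that the rules can be reconciled. Worsening is an AE. Item 1 of the same exclusion list covers only disease that does not become more severe. Item 5 could then be meant for persisting thrombocytopenia or unchanged baseline bleeding, with the doubt rule settling the rest in favour of recording. On that view, omitting a new or worse bleed needs the less natural reading. This stands in part: the plan leans towards recording. It does not remove the conflict, because item 5 is not limited in that way.

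Several stronger conclusions are tempting, and the documents do not support them:

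- *The plan requires bleeds to be omitted.* It does not; it permits omission under one of two rules.
- *Serious bleeds will go unreported.* The SAE definition has no such exclusion, so this rests only on the wording of two explanatory clauses.
- *A bleed in a patient outside the efficacy set leaves no trace.* Section 5.3 keeps patients who drop out after at least one dose in the tolerability analysis, and a bleed that stops treatment fits the worst tolerability category.
- *The hemorrhagic-syndrome task has no plan at all.* Section 10.5 ties presentation of results to the study tasks, and 10.1 offers the McNemar test or a marginal homogeneity test for before-and-after categories. The output is not named, which is a narrower gap.

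It is also fair that the range of 1 to 3 patients is invented, and that this single-arm trial plans no comparison between sites.

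**Conclusion.** Wrong as written, because the rules contradict each other; severity is minor to moderate. Item 5, applied literally, allows a new or worse post-dose bleed to be left out of the AE frequency. The size is 2.5 points per such patient at N = 40 and 2.8 at N = 36, if the bleed is that patient's only event. How many patients this would affect cannot be derived from the documents.

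For patients outside the efficacy set, the bleed would then be visible only within a composite tolerability category, and no named table in 10.3.4 would recover it. A reader might infer that the non-inferiority conclusion is at risk. It is not: AE classification does not enter the definition of response, the primary test or the sample size.

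**What to change.** Replace item 5 in section 9.3 with:

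> *Absence of a platelet response is not in itself an AE. Any bleeding that is new in site or type, or more severe than before the first infusion (by 6.5.5 grade, CTCAE grade or investigator judgement), is recorded as an AE, and as an SAE if it meets any SAE criterion, whether or not attributed to insufficient effectiveness.*

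The 6.5.5 grade alone would not be enough. Its top category covers both gum and gastrointestinal bleeding, so a new gastrointestinal bleed in a patient already graded severe would show no change.

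In section 10.3.4, add a table of the worst post-dose hemorrhagic grade against the Day 0 pre-infusion grade, in all dosed patients (the ITT set of 10.4), with number and percent new or worse. Mark grades that come from telephone or video visits.

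The cost is one replaced item, one table and some additional AE entries. Section 6.6 already schedules the examination before each infusion and at the later visits, so no new procedure is needed. Grades at Visits 4 and 5 will be less reliable when those visits are remote, because petechiae and ecchymoses are hard to count or measure that way.
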